## Analysis Plan

---

### 15.2.1.10. Effort Expenditure for Reward Task

The EEfRT task is a multi-trial game in which participants are given an opportunity on each trial to choose between two different task difficulty levels in order to obtain monetary rewards. Patients are required to complete the task with a specific number of button responses within a constrained period of time in order to obtain a monetary reward. The outcome measures of the EEfRT are:

- Preference (hard or easy task)
- Completion rates

These measures will be provided by the vendor data and will be used in the analysis described below.

Additionally, there will be a series of checks on the data to insure validity of the data used in the analysis. Only subjects with data meeting the following criteria will be used in the analysis.

- Proportion of completed tasks > 75%.
- No more than 10 failed tasks in a row, which would suggest the subject 'took a break'.
- The subject does not time out on >10% of trials
- Average reaction times of  $\geq 500$ ms (0.5s).

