#### 15.2.1.9. Probabilistic Reward Task

The PRT is a measure of reward learning consisting of trials in which patients are asked to respond to two hardly distinguishable cues, of which one is more frequently rewarded. Patients complete a total 300 trials in 3 blocks of 100. Response bias for the rewarded category is the main outcome of interest (Pizzagalli, et al, 2008). In addition, the following outcome measures will be provided:

- Discriminability (subject's ability to differentiate between the two cues)
- Reaction time
- Accuracy (hit rates)

All measures will be computed and provided by the vendor in the source data for each block and as an overall total. The response bias and discriminability measures will also have log-linear adjusted values provided. The adjusted values for response bias and discriminability and original values for reaction time and hit rates at each block will be utilized in the analyses.

Additionally, there will be a series of checks on the data to insure validity of the data used in the analysis. Only subjects with data meeting the following criteria will be used in the analysis.

- The number of valid trials is >80% for each block
- Reward ratio of rich:lean is greater than 25:10 (ratio: 2.5) in each block.
- The number of rich rewards is between 24 and 30, inclusively.
- The number of lean rewards is between 7 and 10, inclusively.
- The lean accuracy in each block is greater than or equal to 40%.
- The rich accuracy in each block is greater than or equal to 40%.
- For combination of blocks e.g. Main, Total: If one block is not usable, then the combo is not usable (i.e. if block 2 is not usable, then total is not usable).

---

Document:	C:\Users\q718413\Documents\NEP-MDD-201_SAP_v1.0_Final_06Dec2018.docx		
Author:	[name]	Version Number:	1.0
		Version Date:	06Dec2018

Template No: CS\_TP\_BS016 Revision 4  
Effective Date: 01Apr2016

Reference: CS\_WI\_BS005

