15.2.3.10. Effort Expenditure for Reward Task

Each outcome measure of the EEfRT will be summarized (mean, standard deviation, median, and

---

Document:	C:\Users\q718413\Documents\NEP-MDD-201_SAP_v1.0_Final_06Dec2018.docx		
Author:	[name]	Version Number:	1.0
		Version Date:	06Dec2018

Template No: CS\_TP\_BS016 Revision 4  
Effective Date: 01Apr2016

Reference: CS\_WI\_BS005

Analysis Plan

---

range) by treatment group at each visit. Line plots of means (+/-SD) will also be presented by treatment group and visit.

The analysis of completion rates will use an ANOVA model with a term for treatment to analyze treatment differences at each scheduled visit. The models LS Means and standard errors (SEs) will be presented for each treatment group. The difference in LS Means with corresponding SEs, 95% confidence intervals for differences, and p-values will also be presented. No adjustments will be made for multiple comparisons.

The analysis of preference will be completed utilizing Generalized Estimating Equation (GEE) models. A binary logistic distribution will be used to model the dichotomous outcome of preference at each scheduled visit. At each visit a series of models using a variety of factors will be fit. All models in the series will include explanatory variables reward magnitude, reward probability, and expected value (reward magnitude X probability) as a base. For each series, four models will be fit. The first will include the base variables with the additional variable of interest with no interactions. The next three models will include the same but with an interaction term between the variable of interest and each base variable in order. The variables of interest that will be explored include:

- Age
- Sex
- Treatment
- MADRS Total Score
- SHAPS Score (0 – 14 scoring method)
- DARS Total Score

The parameter estimates, standard error, 95% confidence interval, degrees of freedom and p-values will be presented to for each model.

All data will be listed by treatment and patient.

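### The PRT and EEfRT validity checks cut on outcomes that are then compared by arm, and the SAP text plans no run without them

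*SAP*

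**What the plan says.** **EEfRT.** SAP 15.2.1.10 names two outcomes, preference and completion rates. It then states: "Only subjects with data meeting the following criteria will be used in the analysis". The four criteria are:
- "Proportion of completed tasks > 75" percent;
- "No more than 10 failed tasks in a row", with the remark that a longer run suggests the subject stopped for a while;
- time-outs on at most 10% of trials;
- a mean reaction time of at least 500 ms.

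SAP 15.2.3.10 adds: "The analysis of completion rates will use an ANOVA model with a term for treatment to analyze treatment differences at each scheduled visit".

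**PRT.** SAP 15.2.1.9 has the same 'only subjects' sentence. Its checks cover valid trials, reward ratio and reward counts. They also include "The lean accuracy in each block is greater than or equal to 40" percent and the matching rule for the rich cue. The section equates accuracy with hit rates, and says: "Response bias for the rewarded category is the main outcome of interest". SAP 15.2.3.9 compares hit rates by arm in a model with treatment, block, stimulus and treatment-by-block.

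**Timing.** Both tasks are given before the first dose at Visit 2 and again at Weeks 4 and 8 (Protocol 9.2, 9.5, 9.7).

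**Other runs.** The sensitivity analyses in SAP 15.1.4 concern MADRS only. The PRT and EEfRT subgroup runs in SAP 15.3.4 reuse the main method. Outside the filtered set the SAP text offers only listings of all data. The table shells mentioned in SAP 8 are not available, so an exclusion table may exist there.

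**The concern.** A validity check should ask whether the task was taken properly. Three of these checks also ask how well the patient did, after randomisation, on a quantity that is then compared between arms.

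- The PRT accuracy rules are a floor on hit rates.
- A patient who leans strongly to the rich cue scores low on the lean cue. The lean rule therefore tends to remove patients with high response bias, the main PRT outcome.
- The EEfRT 75% rule is a floor on completion rate if 'completed' means succeeded.

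If the drug improves or worsens performance, the arms can lose different shares of patients. The comparison is then between selected groups. Task performance is a stated secondary objective (Protocol 6.2), and the planned output would not show whether a small difference reflects the drug or the filter.

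The rules are also incomplete. 'Completed' is not defined. For the PRT, the 'only subjects' wording points to removing the patient, while "If one block is not usable, then the combo is not usable" suggests that single blocks can be kept or dropped.

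**Working it through.** **1. What 'completed' means.** SAP 15.2.1.10 says: "Patients are required to complete the task with a specific number of button responses within a constrained period of time". Completing there means succeeding. There is also a separate time-out limit of 10%. If 'completed' meant only 'not timed out', that limit would already force at least 90% and make the 75% rule redundant. Both points favour 'succeeded', but neither is a definition. If it means attempted, only the failed-run rule remains a concern for the EEfRT. The PRT point does not depend on this.

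**2. The plan's own figure.** 44 per arm, effect 0.5 SD, two-sided alpha 0.10, two-sample t-test: power 75.2%, which reproduces the 75% in Protocol 13.1. That figure concerns MADRS. It serves here only as a reference for a 0.5 SD task effect.

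**3. EEfRT, 75% rule alone.** The documents give no task means or SDs, so every input is assumed: beta-distributed completion, equal SD in both arms, drug raising the mean by 0.5 SD. Share kept = (difference in means among those above 0.75) / (difference in means among all).

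| Mean, SD | Excluded placebo / drug | Share kept | Power |
|---|---|---|---|
| 0.80, 0.08 | 25.1% / 13.6% | 67% | 67% |
| 0.80, 0.12 | 29.9% / 16.9% | 66% | 79% |
| 0.85, 0.12 | 18.6% / 10.4% | 78% | 92% |
| 0.90, 0.08 | 5.7% / 4.0% | 96% | 90% |
| 0.90, 0.05 | 0.9% / 0.6% | 98% | 78% |
| 0.95, 0.04 | 0.1% / 0.2% | 102% | not listed |

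Power can rise because truncation also shrinks the SD. For mean 0.80, SD 0.12:
- Without the filter, the difference over its standard error is 0.060 / (0.12 × √(2/44)) = 0.060 / 0.0256 = 2.34.
- With the filter, 44 × 0.701 = 30.8 and 44 × 0.831 = 36.6 patients remain. The SDs of the truncated distributions are 0.063 and 0.068, and the difference is 0.0394. The ratio is 0.0394 / √(0.063²/30.8 + 0.068²/36.6) = 0.0394 / 0.0160 = 2.46.

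The estimate loses a third of its size, yet the test gains slightly. If the drug lowers completion by 0.5 SD in the same case, 30.1% and 49.1% are excluded and 49% of the difference is kept.

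The assumed shape matters too. At mean 0.90, SD 0.10, equal SDs give 92% kept. If the drug arm's spread narrows as its mean rises, 70% is kept, and at 0.80, 0.15 only 44%.

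**4. PRT, 40% rules alone.** Assumed model: logit(rich) = d + b and logit(lean) = d − b, where d is discriminability and b is bias. There are three blocks of 100 trials (SAP 15.2.1.9), with an assumed 50/50 split of cues. Example: d = 0.6, b mean 0.20 (SD 0.25).

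- *Bias effect of +0.5 SD, d fixed.* Patients excluded: 3.6% placebo, 7.5% drug. The response-bias difference goes from 0.1255 to 0.1078 if the patient is dropped (0.1078/0.1255 = 86%), or to 0.1155 if only the block is (92%). Over 27 scenarios, 64–98% (patient) or 77–99% (block) is kept.
- *The same effect on hit rates.* The model has no treatment-by-stimulus term, so the treatment contrast averages rich and lean. A pure bias effect nearly cancels with or without the filter: −0.0020 unfiltered, −0.0008 filtered by patient.
- *Discriminability effect of +0.5 SD, d SD 0.25.* The hit-rate difference goes from 0.0275 to 0.0243 (88%) or 0.0254 (92%). Over 27 scenarios, 75–98% or 82–99% is kept.
- *Both effects together, same example.* Exclusions nearly balance and 97–99% is kept.
- *No drug effect, 44 per arm, nominal 10%.* Rejection rates are 10.0% (response bias) and 9.7% (hit rate).

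**The case against.** The strongest reply is that these are prespecified checks with a stated purpose. A patient who stops responding says little about reward motivation, and restricting the analysis to engaged records is defensible. That stands, and it is why the filtered analyses should remain the main ones. A reader might infer that the filtered set is wrong and should be replaced by an unfiltered one. The documents do not support that, since it would trade one arguable set for another.

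The size is also open. The EEfRT part hangs on an undefined word, the failed-run rule was not simulated, and no calculation applied all checks jointly. If PRT reward counts depend on responses, which the SAP does not say, the reward-count check would already remove some patients with low lean accuracy. The separate effect of the 40% rule would then be smaller than shown. These limits stand.

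Finally, all task data are listed by patient, Protocol 13.2.1 allows further exploratory analyses, and every task comparison is nominal and unadjusted. This lowers the weight of the point, but a listing is not an analysis, and a rerun chosen after unblinding carries less weight than a planned one.

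A reader might also infer an undeclared change from the protocol, because Protocol 13.2.8.3 bases secondary analyses on patients with available data and SAP 3.3 declares no changes. That does not follow: the same protocol section leaves the detail of the task analyses to the SAP.

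**Conclusion.** The point holds as a cheap improvement. The accuracy rules select on an outcome compared by arm, and the lean rule also tends to remove patients high on response bias. The 75% completion rule selects on its own outcome if 'completed' means succeeded. The SAP text plans no analysis without these rules and no count of exclusions by arm.

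If the drug changes task performance, the estimated difference is usually attenuated. How much cannot be derived from the documents. Under the assumptions above it runs from nothing (completion near ceiling) to about half the difference lost (performance near the cut-off).

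Two stronger readings are not supported. One is that the filter creates false positives: when the drug has no effect on the task, the error rate stays at its nominal level. The other is that the filter costs power: for the EEfRT, power ran from 67% to 97% when the drug raised completion and from 51% to 86% when it lowered it, against about 75% unfiltered. The MADRS analysis is not touched.

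**What to change.** Keep the filtered analyses as planned, and amend the SAP as follows.

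- **Sensitivity run (15.2.3.9 and 15.2.3.10).** At Weeks 4 and 8, repeat the completion-rate, hit-rate and response-bias ANOVAs and the four treatment GEE models for preference. Use all FAS patients with available task data, without the completion, failed-run and accuracy cut-offs.
- **Remaining checks.** State which other checks still apply in that run, and drop any that also depends on the patient's responses (for example the reward counts, if they do).
- **Exclusions.** Tabulate them by arm, visit and criterion.
- **Definitions.** Define 'completed', and state whether a failing PRT block removes the block or the patient.

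The cost is SAP wording, one table, a few ANOVA reruns and 4 models × 2 visits = 8 GEE fits, against 6 variables × 4 models × 3 visits = 72 in the full preference series. The downside is noisier data from poorly engaged patients in the sensitivity run, and results shown on two sets.

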### 15.2.2. MISSING DATA METHODS FOR SECONDARY EFFICACY VARIABLE(S)

No missing data imputation will be used for the secondary efficacy variables.

### 15.2.3. ANALYSIS OF SECONDARY EFFICACY VARIABLES

#### 15.2.3.1. MADRS Total Score

The following analyses will be produced for both the investigator-administered MADRS assessment and the computer-administered MADRS assessment in addition to the analyses described above.

The MADRS total score and change from baseline in MADRS total score will be summarized through descriptive statistics (mean, standard deviation, median, and range) by treatment group and visit. The MADRS total score will also be summarized as a categorical variable by classifying the MADRS total score as Normal (0 – 6), Mild Depression (7 – 19), Moderate Depression (20 – 34) or Severe Depression (35 – 60) for each treatment group and visit.

In addition, the difference for each patient between the investigator-administered MADRS total score and the computer-administered MADRS total score will be summarized for each treatment group and visit alongside the 95% confidence interval p-value from a paired t-test.

#### 15.2.3.2. MADRS-6 Subscale

The change from baseline in the investigator-administered MADRS-6 subscale to week 8 will be analyzed using the same method as the primary efficacy endpoint, substituting the baseline MADRS-6 subscale as the covariate in place of the MADRS total score. In addition, the MADRS-6 subscale and the change from baseline in investigator-administered MADRS-6 subscale will be summarized through

---

Document:	C:\Users\q718413\Documents\NEP-MDD-201_SAP_v1.0_Final_06Dec2018.docx		
Author:	[name]	Version Number:	1.0
		Version Date:	06Dec2018

Template No: CS\_TP\_BS016 Revision 4  
Effective Date: 01Apr2016

Reference: CS\_WI\_BS005

Analysis Plan

---

descriptive statistics by treatment group and visit.

15.2.3.3. MADRS Individual Item Scores

The change from baseline for each individual item comprising the investigator-administered MADRS total score to week 8 will be analyzed using the same method as the primary efficacy endpoint, substituting each individual item as covariates in place of the MADRS total score. The investigator-administered MADRS individual item scores and their change from baseline will also be summarized through descriptive statistics by treatment group and visit.

The MADRS individual item scores, total scores and MADRS-6 total scores will be listed for all patients and visits.

15.2.3.4. Hospital Anxiety and Depression Scale subscales

The change from baseline for both the HADS-A total score and HADS-D total score to week 8 will be analyzed using the same method as the primary efficacy endpoint, substituting the baseline HADS-A and HADS-D total score as appropriate as the covariate in place of the MADRS total score. The HADS-A total score and HADS-D total score and change from baseline in HADS-A total score and HADS-D total score will be summarized through descriptive statistics by treatment group and visit. The HADS-A total score and the HADS-D total score will also be summarized as categorical variables using the classification of Normal/Borderline Abnormal/Abnormal described above by treatment group and visit. Finally, the number and percentage of patients within each result category will be presented by treatment group, item and visit.

All HADS-A and HADS-D total scores and individual item scores will be listed.

15.2.3.5. Dimensional Anhedonia Rating Scale

The change from baseline for the DARS total score to week 8 will be analyzed using the same method as the primary efficacy endpoint, substituting the baseline DARS total score as the covariate in place of the MADRS total score. The DARS total score and change from baseline in DARS total score will be summarized through descriptive statistics by treatment group and visit. In addition, the number and percentage of patients within each result category will be presented by treatment group, item and visit. Each DARS dimensions score (Hobbies, Food/Drink, Social Activities, Sensory Experience) and change from baseline in DARS dimensions score will be summarized through descriptive statistics by treatment group and visit.

All DARS individual item scores and total scores will be listed.

15.2.3.6. Snaith Hamilton Pleasure Scale

The change from baseline for the SHAPS total score to week 8 will be analyzed using the same method as the primary efficacy endpoint, substituting the baseline SHAPS total score as the covariate in place of the MADRS total score. The SHAPS total score and change from baseline in SHAPS total score will be summarized through descriptive statistics by treatment group and visit. In addition, the number and percentage of patients who agree or disagree to each question will be presented by treatment group, item and visit.

All SHAPS individual item scores and total scores will be listed.

---

Document:	C:\Users\q718413\Documents\NEP-MDD-201_SAP_v1.0_Final_06Dec2018.docx		
Author:	[name]	Version Number:	1.0
		Version Date:	06Dec2018

Template No: CS\_TP\_BS016 Revision 4  
Effective Date: 01Apr2016

Reference: CS\_WI\_BS005

Analysis Plan

---

15.2.3.7. Response

The difference in the proportion of responders at week 8 between each treatment group will be estimated for each response variable using a logistic regression model with treatment and investigator site as a fixed effect and baseline investigator-administered MADRS total score as a continuous covariate, using Firth's Penalized Likelihood with CI and p-values based on individual Wald tests.

In addition, the number and percentage of patients within each CGI-S and CGI-I result category will be presented by treatment group and visit. Both CGI-S and CGI-I results will be available at the baseline visit, the CGI-I at baseline will refer to the CGI-S assessment at screening. All subsequent CGI-I assessments will refer to the baseline CGI-S assessment.

Results of each response category at week 8 will be listed for all randomized patients. In addition, all CGI-S and CGI-I results will also be listed.

15.2.3.8. The Facial Expression Recognition Task

For each emotion of the FERT, each outcome measure will be summarized (mean, standard deviation, median, and range) by treatment group at each visit. Line plots of means (+/-SD) will also be presented by treatment group and visit. Additionally, accuracy will be summarized by intensity level for each emotion and plotted versus intensity level in scatterplots.

At each scheduled visit, an ANOVA model with a term for treatment will be used to analyze treatment differences. LS Means and standard errors (SEs) will be presented for each treatment group. A second ANOVA model will be fit with additional factors of gender, baseline MADRS total score, and baseline FERT outcome measure. The difference in LS Means with corresponding SEs, 95% confidence intervals for differences, and p-values will also be presented. No adjustments will be made for multiple comparisons.

All data, including the accuracy response for each intensity level, will be listed by treatment and patient.

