8. Proportion of patients who demonstrate significant clinical improvement, where **improvement** is defined by a score of 1 (very much improved) or 2 (much improved) on the CGI-I at Week 8.

The following secondary efficacy endpoints based on the performance tasks will be analyzed and presented in summary and graphical displays.

Data for the FERT will be summarized (mean, standard deviation, range) for each treatment group at each visit. All treatment differences will be estimated with 95% CI. No adjustments will be made for multiple comparisons. The analysis will employ ANOVA models without adjusting for covariates. However, if significant confounds are identified, a secondary analysis will be performed to examine the relationship between FERT outcome measures and other covariates. A full description of the statistical analysis methods for FERT outcome measures will be provided in in the SAP.

9. Outcome measures from the FERT
  - a) Accuracy
  - b) Misclassification
  - c) Average reaction time
  - d) Target sensitivity
  - e) Response bias

Data for all PRT outcome measures will be summarized (mean, standard deviation, range) for each treatment group at each visit. The ANOVA models will be used to compare between treatment groups. For “Response bias” and “Discriminability,” treatment group, block, and treatment-by-block interactions will be considered fixed effects. For “Reaction time” and “Hit rates,” the stimulus type will be included as an additional fixed effect. The details of the analysis methods for these outcome measures will be described in the SAP.

10. Outcome measures from the PRT

- a) Response bias
- b) Discriminability
- c) Reaction time
- d) Hit rates

Data for all EEfRT outcome measures will be summarized (mean, standard deviation, range) for each treatment group at each visit. Statistical analyses of the Preference during the EEfRT trial will be performed using Generalized Estimating Equation (GEE) models. A binary logistic distribution will be used to model the probability of the Preference. The relationship and interactions between Preference and independent variables of reward magnitude, reward probability, expected value, age, sex, and efficacy parameters will be explored. The ANOVA model will be used to compare the completion rates between treatment groups. The details of the analysis method for these outcome measures will be described in the SAP.

11. Outcome measures from the EEfRT

- a) Preference (hard or easy task choice)

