## 6.5. STATISTICAL TESTS

Confidence intervals will be reported at the 95% level and all tests will be two-sided, unless otherwise specified in the description of the analyses. P-values will be presented to identify trends in the study. That is, statistical tests that are significant at the 10% level will be considered as demonstrating a trend

Document: C:\Users\q718413\Documents\NEP-MDD-201\_SAP\_v1.0\_Final\_06Dec2018.docx  
 Author: [name]  
 Version Number: 1.0  
 Version Date: 06Dec2018

Template No: CS\_TP\_BS016 Revision 4  
 Effective Date: 01Apr2016  
 Reference: CS\_WI\_BS005

Copyright © 2009, 2010, 2012, 2016 Quintiles Transnational Corp. All rights reserved.  
 The contents of this document are confidential and proprietary to Quintiles Transnational Corp. Unauthorized use, disclosure or reproduction is strictly prohibited.

Analysis Plan

---

and statistical tests that are significant at the 5% level will be considered as demonstrating a strong trend.

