15.2.1.8. The Facial Expression Recognition Task

The FERT is a computer test used to assess attention to, and perception of, social cues and affective

---

Document:	C:\Users\q718413\Documents\NEP-MDD-201_SAP_v1.0_Final_06Dec2018.docx		
Author:	[name]	Version Number:	1.0
		Version Date:	06Dec2018

Template No: CS\_TP\_BS016 Revision 4  
Effective Date: 01Apr2016

Reference: CS\_WI\_BS005

Analysis Plan

---

information. Faces with 6 different basic emotions (happiness, fear, anger, disgust, sadness, surprise) are displayed on the screen and the patient is required to indicate the expression of the face via a button-press. Different intensity levels (10) of each emotion are presented, which increases the ambiguity of the facial expression and the sensitivity of the task (Harmer et al, 2009). In addition, neutral faces will be displayed on screen during the task and is a button-press option. Intensity levels do not apply to the neutral face but the 5 outcome measures will be reported for neutral faces as well.

There are 5 outcome measures from the FERT for each emotion. They are:

- Accuracy (%)
- Misclassification (%)
- Average reaction time (ms)
- Target sensitivity
- Response bias

These measures, along with the accuracy response for each intensity level, for each emotion will be provided by the vendor data and will be used in the analysis described in [section 15.2.3.8](#).

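### The SAP turns the protocol's conditional covariate analysis of the FERT into a standing second model, does not say which model the trend rule applies to, and declares no change.

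*SAP*

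**What the plan says.** **Protocol 13.2.8.3** ranks the FERT analyses. The main one is unadjusted: "The analysis will employ ANOVA models without adjusting for covariates". Covariates come in only under a condition: "if significant confounds are identified, a secondary analysis will be performed to examine the relationship between FERT outcome measures and other covariates". The same paragraph leaves the full description of FERT methods to the SAP.

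**SAP 15.2.3.8** starts from the same model: "At each scheduled visit, an ANOVA model with a term for treatment will be used to analyze treatment differences". It promises LS means and standard errors by arm, and then adds, with no condition: "A second ANOVA model will be fit with additional factors of gender, baseline MADRS total score, and baseline FERT outcome measure". The next sentence reads: "The difference in LS Means with corresponding SEs, 95% confidence intervals for differences, and p-values will also be presented". It does not say whether that covers one model or both. Neither model is called primary or supportive, and no multiplicity adjustment is made.

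**SAP 6.5** sets the rule for reading p-values: "statistical tests that are significant at the 10% level will be considered as demonstrating a trend". **SAP 3.3** states that no changes from the protocol are planned.

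**SAP 15.2.1.8** gives the scope: "There are 5 outcome measures from the FERT for each emotion". There are six emotions, and the same measures are reported for neutral faces. The protocol's schedule of assessments places the FERT at baseline, Week 1 and Week 2.

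**The concern.** The FERT belongs to the third secondary objective. The SAP gives each FERT measure two models at a visit and does not say which one is the result. If they fall on opposite sides of 10%, a reader cannot tell from the SAP whether a trend has been shown, and the choice could be made after unblinding. Treating the protocol's ranking as still in force settles that question, but then the lead model discards a baseline FERT score that every patient is scheduled to provide before dosing. Either way the SAP's planned analysis differs from the protocol's, and the section reserved for such differences is empty.

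**Working it through.** **Inputs from the documents.** Two-sided tests and a 10% trend level (SAP 6.5). Five measures for seven face categories (SAP 15.2.1.8). Two post-baseline FERT visits (protocol Table 1). Randomization of about 50 per arm, with 44 per arm used for sizing (protocol 13.1).

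**Assumed inputs.** The documents give no correlation R between the post-baseline FERT outcome and the model covariates, and no FERT effect size. R is varied below. The effect is set at 0.4 SD with 45 patients per arm.

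**The plan's own figure.** The only related calculation in the plan is the primary-endpoint sizing. With effect size 0.5, 44 per arm and two-sided 10%, the noncentrality is 0.5 × √(44/2) = 2.345 on 86 degrees of freedom, giving power of 75.2%. The stated 75% is reproduced. The plan states no error rate for the pair of FERT models.

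**Step 1: precision.** Adjusting for covariates with correlation R shrinks the residual SD by √(1 − R²), so the effect of 0.4 becomes 0.4/√(1 − R²). With noncentrality (that effect) × √(45/2) and two-sided 10%:

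| Model | Effective effect | Noncentrality | Power |
|---|---|---|---|
| Unadjusted | 0.400 | 1.90 | 59% |
| Adjusted, R = 0.4 | 0.436 | 2.07 | 66% |
| Adjusted, R = 0.5 | 0.462 | 2.19 | 70% |
| Adjusted, R = 0.6 | 0.500 | 2.37 | 76% |
| Adjusted, R = 0.7 | 0.560 | 2.66 | 84% |

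**Step 2: false trends under an either-model reading.** With no effect, the two treatment statistics are approximately bivariate normal with correlation √(1 − R²). The chance that at least one falls outside ±1.645 is:

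| R | Correlation of the two statistics | Either p < 0.10 |
|---|---|---|
| 0.2 | 0.980 | 11.7% |
| 0.3 | 0.954 | 12.5% |
| 0.4 | 0.917 | 13.3% |
| 0.5 | 0.866 | 14.2% |
| 0.6 | 0.800 | 15.1% |
| 0.7 | 0.714 | 16.0% |
| 0.8 | 0.600 | 16.9% |
| 0.9 | 0.436 | 17.9% |

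A simulation of both models with 44 per arm and R from 0.3 to 0.8 agrees. Each model alone rejects 9.8% to 10.3% of the time, and at least one rejects 12.5% (R = 0.3) to 16.7% (R = 0.8). These rates are per measure per visit.

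**Step 3: scale.** 7 face categories × 5 measures × 2 visits = 70 comparisons. Reading one model gives 70 × 0.10 = 7 expected chance trends if no effect exists. An either-model reading gives 70 × 0.133 = 9.3 at R = 0.4 and 70 × 0.160 = 11.2 at R = 0.7.

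**The case against.** - **The documents do rank the models.** A reader of SAP 15.2.3.8 alone might infer that the FERT has no lead model. Across the two documents that is not so. The protocol makes the unadjusted ANOVA the analysis, SAP 3.3 declares no change, and the SAP itself calls the adjusted fit the second model. This stands. It does not close the matter, because the protocol delegates the full FERT methods to the SAP, which drops the condition and does not restate the order.
- **Two p-values per comparison are not established.** One might infer 140 p-values (70 × 2). The sentence promising differences and p-values follows the second model and could refer to that model alone. The text is ambiguous, so a double test is possible but not shown.
- **The trend rule is not shown to run above 10%.** SAP 6.5 applies to each test, and each test holds about 10%. The 12% to 18% range needs an either-model reading that no section states, plus a correlation that the documents do not give. The SAP does not exclude that reading either.
- **An unadjusted FERT model is consistent with the other tasks.** The PRT models and the EEfRT completion-rate model in the SAP also have no baseline term. That is true. HADS, DARS and SHAPS do adjust for their own baseline, and for the FERT the adjusted model is already planned.
- **The consequence is modest.** These are secondary, nominal p-values in a Phase 2a study that openly forgoes multiplicity control. The 7 chance trends expected from one model outnumber the 2 to 4 that a second model would add at R = 0.4 to 0.7. This stands, and it limits the weight of the point.

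**Conclusion.** The point holds as a mismatch between protocol and SAP with an unassigned trend label. A conditional secondary analysis has become an unconditional second model, the SAP does not tie its trend rule to either model, and SAP 3.3 does not record the change.

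The size depends on how the gap is read:

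- **Protocol order kept:** the error rate is 10% per test, but the lead model is the less precise one. The loss is about 7 to 25 percentage points of power (59% against 66% to 84%), assuming a 0.4 SD effect, 45 per arm and R of 0.4 to 0.7.
- **Either model allowed:** the false-trend chance is about 12% to 18% per measure per visit for R of 0.2 to 0.9. This is conditional on a reading that the SAP neither states nor excludes.

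The primary endpoint and the sample size are unaffected.

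**What to change.** Before unblinding, amend the SAP wording in three places.

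1. In 15.2.3.8, name the model with gender, baseline MADRS and baseline FERT as the lead FERT analysis at Weeks 1 and 2. State that its difference, confidence interval and p-value are the FERT result. Limiting it to post-baseline visits also avoids adjusting the baseline measure for itself, which the present reference to each scheduled visit would allow.
2. In the same section, label the treatment-only model supportive and state that SAP 6.5 applies only to the lead model. Its p-values need not be suppressed.
3. In 3.3, list this as a change from protocol 13.2.8.3, with the reason: it uses a pre-dose score already collected and is expected to be more precise.

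No new data or procedures are needed. The cost is a declared departure from the protocol's unadjusted analysis. Naming a single FERT measure and visit would address the separate matter of the 70 comparisons. That is a trade-off for the sponsor and is not needed to resolve this point.
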